**Figure 1 Study Design**

AD=atopic dermatitis; IMP=investigational medicinal product; EP=endpoint; EASI=eczema area and severity index; IGA= investigator global assessment; LTE=long-term extension; Q4W=every 4 weeks; NA=not applicable.

On Day 169 (Week 24), patients are re-randomised prior to IMP administration on the basis of their Day 169 (Week 24) response.

### 3.2. Treatments

#### KY1005

[REDACTED]

#### Matching Placebo

[REDACTED]

#### 4. General Statistical Considerations

Continuous data will be summarized using descriptive statistics (i.e., n, mean, standard deviation (SD), median, minimum, and maximum). Categorical data will be summarized using the patient count and percentage in each category.

##### For Part 1:

The data in Part 1 will be presented according to planned treatment or actual treatment received at Day 1. These analyses include the following: patient disposition, demographics and baseline characteristics, significant protocol deviations, medical history, drug exposure, prior/concomitant medications for AD and non-AD, rescue and prohibited medications and procedures impacting efficacy, rescue medications, prohibited medications and procedures, concomitant procedures, adverse events, injection site reactions, efficacy parameters (EASI, IGA, NRS etc), 12-lead electrocardiogram parameters, laboratory parameters, PK parameters, and ADA.

##### For Part 2:

The data in Part 2 will be presented according to treatment sequence planned or received. These analyses include the following: drug exposure, prior/concomitant medications for AD and non-AD, rescue and prohibited medications and procedures impacting efficacy, rescue medications, prohibited medications and procedures, concomitant procedures, adverse events, injection site reactions, efficacy parameters (EASI, IGA, NRS etc), 12-lead electrocardiogram parameters, laboratory parameters, PK parameters, and ADA. Patient disposition, demographics and baseline characteristics, significant protocol deviations, and medical history will be presented among patients enrolled in Part 2. Data on some endpoints such as prior/concomitant medications for AD and non-AD, rescue and prohibited medications and procedures impacting efficacy, rescue medications, prohibited medications and procedures, concomitant procedures, efficacy adverse events, laboratory parameters, PK and ADA will be presented from baseline up to Week 52 or Week 68 among patients enrolled in Part 2. In addition, presentation of rescue and prohibited medications and procedures will also be done for Week 52 to Week 68 data only.

All CIs presented will be 95% (two-sided) CIs.

Non-zero percentages will be rounded to one decimal place. When count data are presented, percentages will be rounded to one decimal place. If count is 0, the percentage will not be presented. CI will be presented to two decimal places for proportion, wherever applicable. A row denoted "Missing" will be included in count tabulations where specified on the shells to account for dropouts and missing values.

The denominator for all percentages will be the number of patients with non-missing values of corresponding parameter in that treatment within the analysis population of interest, unless otherwise specified.

For the summary statistics of all numerical variables, unless otherwise specified, minimum and maximum will be displayed to the same level of precision as reported up to a maximum of three decimal places. Mean and median will be displayed to one level of precision greater than the data collected up to a maximum of three decimal places. Standard deviation / standard error will be

displayed to two levels of precision greater than the data collected up to a maximum of three decimal places.

A table, figure, listing is to be generated for any required item even where no data is available or reported. This will ensure the health authorities that the tables, figures, listings and narratives are accounted for. This table, figure or listing will state: “No Data Reported”.

All other statistical analyses performed in part 1 will be performed using a two-sided hypothesis test at the overall 5% level of significance.

P-values will be rounded to four decimal places. If a rounded P-value is less than 0.0001 it will be reported as “<0.0001.”

Unless otherwise specified, baseline will be defined as the last non-missing evaluation prior to study drug administration.

#### Calculation of Change and Percent Change from Baseline

Change from Baseline to any trial Week t ( $C_t$ ) is calculated as follows:

$C_t = M_t - M_B$ , where:

- $M_t$  is the measurement of interest at Week t
- $M_B$  is the measurement of interest at Baseline

Percent change from Baseline to any trial Week t ( $P_t$ ) is calculated as follows:

$$P_t = 100*(C_t/M_B)$$

### 4.1. Sample Size

[figure not shown]
A sample size of 350 patients (70 patients / group) in the target population, (adult with moderate-to-severe AD who have a documented history, within 6 months prior to Baseline, of either inadequate response to topical treatments or inadvisability of topical treatments), randomised 1:1:1:1 to four KY1005 groups or matching Placebo group is estimated to provide at least [REDACTED] power to detect a pairwise difference in means between each KY1005 and Placebo with respect to the percentage change in EASI from Baseline to Day 113 (Week 16), based on a 2-sided 2-sample equal-variance t-test.

[REDACTED]

### 4.2. Intercurrent Event

Intercurrent events relevant for this study are presented in table below:

**Table 2 Intercurrent Event Types**

### 4.3. Analysis Set

The following analysis sets will be used in the statistical analyses.

#### 4.3.1. All Enrolled Set

All Enrolled Analysis Set includes all patients who signed an informed consent form with no screen failures. Analysis will be based on treatment allocated at randomisation.

#### 4.3.2. Full Analysis Set for Part 1

The Full Analysis Set (FAS1) for Part 1 includes all randomised patients up to week 24. Efficacy analysis will be based on treatment allocated at randomisation.

#### 4.3.3. Full Analysis Set for Part 2

The Full Analysis Set (FAS2) for Part 2 includes all re-randomised patients at Week 24 up to week 52. Efficacy analysis will be based on treatment allocated at re-randomisation.

#### 4.3.4. Safety Analysis Set for Part 1

The safety set (SAF1) for Part 1 will consist of all patients who take at least one dose of study treatment, including Placebo up to week 24. Any analysis based on the SAF1 will be based on the treatment actually received, regardless of assigned treatment according to the planned randomisation.

#### 4.3.5. Safety Analysis Set for Part 2

The safety set (SAF2) for Part 2 will consist of all re-randomised patients at Week 24 who take at least one dose of study treatment on or after Week 24. Any analysis based on the SAF2 will be based on the treatment actually received at week 24, regardless of assigned treatment according to the planned randomisation.

#### 4.3.6. Pharmacokinetic Set for Part 1

The PK set will consist of all randomized patients in the SAF1 with at least one post-Baseline PK sample (with adequate documentation of dosing and sampling dates and times) up to week 24. Any analysis based on the PK1 will be based on the treatment actually received, regardless of assigned

treatment according to the planned randomisation. Patients who received only placebo will not be included.

#### **4.3.7. Pharmacokinetic Set for Part 2**

The PK set will consist of all randomized patients in the SAF2 with at least one post-Baseline PK sample (with adequate documentation of dosing and sampling dates and times) from Week 24 up to week 52. Any analysis based on the PK2 will be based on the treatment actually received at week 24, regardless of assigned treatment according to the planned randomisation. Patients who received only placebo will not be included.

#### **4.3.8. Anti-drug Antibody Set for Part 1**

The ADA set will consist of all randomized patients treated with KY1005 in the SAF1 with at least one post-Baseline ADA result (positive, negative or inconclusive) up to week 24. Any analysis based on the ADA1 will be based on the treatment actually received, regardless of assigned treatment according to the planned randomisation.

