6.5 Pharmacokinetic and Anti-drug Antibodies Assessments

6.5.1 Pharmacokinetic Procedures

Blood samples will be withdrawn periodically for KY1005 assay. Pharmacokinetic and ADA samples will be collected from all patients including those receiving Placebo.

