10.3.2 Safety Set

The safety set (SAF) will consist of all patients who take at least one dose of study treatment, including Placebo. Safety analysis will be based on actual treatment received.

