10.3.4 Anti-drug Antibody Set

The ADA set will consist of all randomised and treated patients in the SAF with a Baseline ADA result (positive, negative or inconclusive) and at least one post-Baseline ADA result (positive, negative or inconclusive).

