#### **4.3.9. Anti-drug Antibody Set for Part 2**

The ADA set will consist of all randomized patients treated with KY1005 in the SAF2 with at least one post-Baseline ADA result (positive, negative or inconclusive) from Week 24 up to week 52. Any analysis based on the ADA2 will be based on the treatment actually received at week 24, regardless of assigned treatment according to the planned randomisation.

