### 10.3. Immunogenicity

All the analysis will be performed using Anti-drug Antibody Sets.

Patient's ADA status, response variable and kinetics of ADA responses (see definitions below) will be summarized on the ADA population.

Kinetics of ADA responses will be described for patients with treatment-induced ADA and for patients with treatment-boostered ADA, separately. Time to ADA onset and duration of ADA will be described with minimum, Q1, median, Q3 and maximum statistics.

Peak titer will be described with minimum, Q1, median, Q3 and maximum statistics for patients with treatment-induced ADA and for patients with treatment-boostered ADA, separately.

Sample status (negative, positive, inconclusive) will be described using descriptive statistics.

The impact of positive immune response on efficacy, PK and safety variables may be further explored, depending on ADA incidence.

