#### Patient's ADA status

- Patients with **pre-existing ADAs** correspond to patients with ADAs present in samples drawn before first administration of intervention. Patients with missing ADA sample at baseline will be considered as without pre-existing ADA.
- Patients with **treatment-emergent ADA** correspond to patients with at least one treatment-induced/boostered ADA.
- Patients with **treatment-induced ADAs** correspond to patients with ADAs that developed during the treatment-emergent (TE) period and without pre-existing ADA (including patients without pre-treatment samples).
- Patients with **treatment-boostered ADAs** correspond to patients with pre-existing ADAs that are boosted during the TE period to a significant higher titer than the baseline. A 2-fold serial dilution schema is used during titration, so at least a 4-fold increase will be considered as significant.
- Patients with **unclassified ADA** correspond to patients with pre-existing ADAs that cannot be classified as treatment-boostered ADA because of missing titer(s) (ie, a positive ADA sample during the TE period in a patient with pre-existing ADA but with missing titer at this sample or at baseline).

- Patients **without treatment-emergent ADA** correspond to patients without treatment-induced/boosted ADA and without any inconclusive sample nor unclassified ADA during the TE period.
- Patients **with inconclusive ADA** are defined as patients which cannot irrefutably be classified as with or without treatment-emergent ADA.

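### The SAP's ADA sets leave out placebo patients whom the protocol includes and samples, so no concurrent placebo rate of new ADA positivity will be reported (minor; cheap to fix)

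*SAP*

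**What the plan says.** **Protocol.** Section 10.3.4 defines the ADA set as "all randomised and treated patients in the SAF with a Baseline ADA result (positive, negative or inconclusive) and at least one post-Baseline ADA result". The safety set from which it is drawn (10.3.2) "will consist of all patients who take at least one dose of study treatment, including Placebo". Section 6.5.1 adds: "Pharmacokinetic and ADA samples will be collected from all patients including those receiving Placebo". Section 10.4.4 names the endpoint as antibody titre and number of positive patients, summarised by visit and treatment regime, and leaves the statistical analysis to the SAP.

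**SAP.** Section 4.3.8 reads: "The ADA set will consist of all randomized patients treated with KY1005 in the SAF1 with at least one post-Baseline ADA result". Section 4.3.9 reads: "The ADA set will consist of all randomized patients treated with KY1005 in the SAF2 with at least one post-Baseline ADA result". Neither asks for a baseline result. Section 10.3 opens with: "All the analysis will be performed using Anti-drug Antibody Sets". On missing baselines it says: "Patients with missing ADA sample at baseline will be considered as without pre-existing ADA". Its definition of treatment-induced ADA expressly admits patients with no pre-treatment sample, and ADA incidence is the proportion with treatment-induced or treatment-boosted ADA in the treatment-emergent period.

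**The concern.** The same secondary endpoint has two different populations. The protocol's includes placebo and the SAP's does not, and no other visible SAP output reports placebo ADA.

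This matters because some ADA positivity over repeated sampling is not caused by the drug: assay false positives that survive confirmation, and seroconversion for other reasons. Treated placebo patients, sampled on the same schedule with the same assay, measure that background directly. Without them, an ADA incidence on KY1005 has no concurrent reference, and a comparison across the four regimens has no zero-dose point.

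The result is used beyond its own table. SAP 10.2 splits the serum concentration summaries by ADA status, SAP 10.3 allows exploration against efficacy, PK and safety, and SAP 12 builds the interim ADA sets from the definitions in 4.3.

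The second difference, the dropped baseline requirement, works through the missing-baseline rule. A KY1005 patient with antibodies already present, but with no baseline sample, is counted as treatment-induced if a later sample is positive.

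**Working it through.** The plan states no ADA rate, missing-baseline rate or ADA sample size, so there is no figure to reproduce. The check sets the definitions side by side and then gives illustrative arithmetic.

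**Definitions**
- Placebo: included in protocol 10.3.4 (through 10.3.2); excluded in SAP 4.3.8 and 4.3.9.
- Baseline result: required in protocol 10.3.4; not required in either SAP section.
- Post-baseline result: at least one, in both documents.
- Samples on placebo: collected (protocol 6.5.1).
- Analyses outside the ADA sets: none (SAP 10.3).

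**Patients left out.** With 350 randomised equally to five arms, about 70 are on placebo and 280 on KY1005. The SAP Part 1 set omits 70/350 = 20% of those randomised.

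**Illustrative background** (assumed per-patient rate *b* of new positivity without any drug effect). Expected positives are 280*b* on KY1005 and 70*b* on placebo. The chance of at least one placebo positive is 1 − (1 − *b*)^70.
- *b* = 1%: 2.8 on KY1005, 0.7 on placebo, chance 51%.
- *b* = 3%: 8.4 on KY1005, 2.1 on placebo, chance 88%.
- *b* = 5%: 14 on KY1005, 3.5 on placebo, chance 97%.

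If no placebo patient were positive, the exact two-sided 95% upper bound on the background would be 1 − 0.025^(1/70) = 5.1%.

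**Why the pre-dose sample is only a partial substitute.** It is a single draw, whereas SAP Table 15 lists four post-baseline ADA visits in Part 1 (Weeks 2, 4, 16 and 24). With an assumed false-positive rate *f* per sample, and samples assumed independent within a patient, the chance of at least one positive is 1 − (1 − *f*)^4. At *f* = 1% this is 3.9%, about 11 of 280. Independence is the unfavourable case. If reactivity persists within a patient, many of these patients would already be positive before dosing, and SAP 10.3 would then require at least a 4-fold titre rise to count them. The pre-dose sample does not show where between these cases the trial lies; placebo patients followed over time would.

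**Missing-baseline rule.** Spurious treatment-induced patients = 280 × (share with no baseline sample) × (rate of pre-existing or false-positive ADA). Both inputs are assumed to lie between 1% and 10%.
- Low end: 280 × 0.01 × 0.01 = 0.03 patients (0.01 percentage points).
- High end: 280 × 0.10 × 0.10 = 2.8 patients (1.0 percentage point).

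**The case against.** Four arguments against the point have weight.

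1. **KY1005 patients supply their own background.** The SAP still classifies pre-existing ADA from Week 0 samples in up to about 280 patients, four times the placebo arm. A pre-dose count of 0/280 would bound single-sample positivity at 1 − 0.025^(1/280) = 1.3%, tighter than the 5.1% from 0/70. This stands, so one should not infer that a low incidence on KY1005 could not be told from background at all. What is missing is narrower: the concurrent rate of new positivity across repeated samples.

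2. **The SAP has authority here.** Protocol 10.4.4 defers the analysis to it, the version history records that some Section 4.3 definitions were refined in version 2.0, and the body of the SAP's section on changes to the planned analysis is not shown. A reader might infer an undeclared or unexplained departure; the documents do not support that. A declared change would still leave the comparator missing.

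3. **Protocol intent is unclear.** Section 10.3.3 builds the PK set from the safety set in the same generic way, although the synopsis confines the PK endpoint to patients receiving KY1005. Sampling everyone in a blinded trial does not prove that a placebo ADA analysis was intended. That is fair, but the definition as written includes placebo and the samples will exist.

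4. **The missing-baseline rule is explicit and conservative.** It can only raise incidence, and excluding these patients could discard true seroconverters. This stands and is why the rule is kept in the fix. A reader might also infer that every patient without a baseline sample is counted as treatment-induced. SAP 10.3 does not say that: ADA must be found in the treatment-emergent period, so an ADA-negative patient is never counted.

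**Conclusion.** The point holds in a limited form. The protocol's ADA set includes placebo; the SAP's sets do not, and every SAP immunogenicity analysis uses those sets. The trial will therefore report ADA incidence on KY1005 without a concurrent placebo rate, although placebo samples are planned.

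The size cannot be established from the documents. The figures of about 3 to 14 of 280 rest on an assumed 1% to 5% per-patient background, and the 3.9% repeated-sample figure also rests on independence between samples. The missing-baseline rule is the smaller issue, at most about 1 percentage point over the assumed ranges.

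The endpoint is descriptive and no efficacy inference depends on it. This is a cheap improvement of minor severity.

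**What to change.** - Amend SAP 4.3.8 and 4.3.9 together, so that each set includes treated placebo patients with at least one post-baseline ADA result. Changing only 4.3.8 would leave two ADA populations within one SAP.
- Report ADA incidence in SAP 10.3 with placebo as its own column beside each KY1005 regimen. In Part 2, that column should hold patients on placebo since Day 1, not those withdrawn from KY1005 to placebo, who have been exposed to the drug.
- Keep the missing-baseline rule, and add a sensitivity incidence restricted to patients with a baseline ADA result, which matches the protocol set.
- If the sponsor prefers KY1005-only sets, state the reason for departing from protocol 10.3.4 and still tabulate placebo ADA alongside.

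The cost is SAP wording, one extra table column, one sensitivity table, and assaying placebo samples whose collection is already planned.

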#### **4.3.9. Anti-drug Antibody Set for Part 2**

The ADA set will consist of all randomized patients treated with KY1005 in the SAF2 with at least one post-Baseline ADA result (positive, negative or inconclusive) from Week 24 up to week 52. Any analysis based on the ADA2 will be based on the treatment actually received at week 24, regardless of assigned treatment according to the planned randomisation.

### **4.4. Other Important Considerations**

#### **4.4.1. Definition of Study Period to be evaluated**

For the purposes of efficacy and safety data analysis, and for reporting, the following study periods are considered:

- Part 1:
  - For efficacy data, this is the induction phase which encompasses data from baseline through week 24 visit.
  - For non-efficacy data, this is the induction phase which encompasses data from baseline through end of study involvement for patients who did not proceed to Part 2 or first IMP date or rerandomization date in Part 2 for patients who proceed to Part 2.
- Part 2:
  - For efficacy data, this is the maintenance phase which encompasses data from week 24 up to week 52 visit.
  - For non-efficacy data, this is the maintenance phase which encompasses data from first IMP date or rerandomization date in Part 2 up to week 68. For rescue and prohibited medications and procedures impacting efficacy, this includes data from first IMP data or rerandomization date in Part 2 up to week 52.
- Overall:
  - For efficacy data, this is the period covering from baseline to week 52 visit.
  - For safety data, this is the period covering from baseline through end of study involvement for patients who did not proceed to Part 2 or up to week 68 for

patients who proceed to Part 2. For rescue and prohibited medications and procedures impacting efficacy, this includes data up to week 52 only.

For efficacy analysis, all observed measurements will be eligible to be included in analyses.

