#### **4.4.2. Windows Periods**

Before analyzing the data, all post-Baseline visits (scheduled or unscheduled, unless specified otherwise) will be mapped to an analysis visit based on the windowing algorithm in Section 15.5 Analysis window Details. If multiple visits containing the same data of interest can be mapped to the same analysis visit, the visit closest to the target day will be used in the analysis. In the event that two or more visits are equidistant to the target day, the later visit will be used in the analysis.

Please refer Section 0 for details of Analysis Window.

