# Early Termination Visit could be done by the Investigator (see Section 3.4, Section 3.5 and Section 9 of protocol).

a On IMP administration days, all assessments, including taking blood samples, will be performed pre-injection unless stated otherwise.

b On IMP administration days vital signs will be measured pre-injection and 30 minutes post injection. The tolerance on vital signs after dosing is ±5 minutes.

c [REDACTED]

d NRS (pruritus) will be recorded daily, ideally in the morning, based on the previous 24 hours with worst (maximum) itch intensity recorded.

e Where IMP administration occurs on a re-randomisation day the IMP injection is to be administered after re-randomisation (with the new regimen where applicable).

f [REDACTED]

g Where possible, the PRO assessments completed at the study site are to be completed by patients prior to the completion of other study assessments and the administration of IMP.

h A telephone visit is defined as a videoconference, video call or telephone call.

i If urine pregnancy test is positive, a serum control must be done before IMP administration

j [REDACTED]

- k The ICF from the DRI/Phase2b/parent study will not be valid as LTE informed consent. In order for patients to roll over to the LTE study, a specific LTE ICF will need to be applied, agreed upon and signed at the LTE study, as the LTE is a separated protocol.

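### The re-randomisation date belongs to both Part 1 and Part 2 for safety, and the Week 24 efficacy windows do not stop there, so some data from after the Part 2 dose can be analysed as Part 1

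*SAP*

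**What the plan says.** **Non-efficacy data.** In SAP 4.4.1, Part 1 closes at the "first IMP date or rerandomization date in Part 2 for patients who proceed to Part 2", and Part 2 covers "data from first IMP date or rerandomization date in Part 2 up to week 68". Neither bound is marked exclusive or tied to the time of the injection, and the text does not say which date applies if the two differ. SAP 9.1 treats TEAEs in the same way. Period 1 runs to the Week 24 visit, and Period 2 takes any event whose start date is on or after the first Part 2 IMP or re-randomisation.

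**Efficacy data.** SAP 4.4.1 says of Part 1 that "this is the induction phase which encompasses data from baseline through week 24 visit" and of Part 2 that "this is the maintenance phase which encompasses data from week 24 up to week 52 visit". It adds: "For efficacy analysis, all observed measurements will be eligible to be included in analyses". SAP 4.4.2 maps scheduled and unscheduled visits to analysis visits and keeps the one closest to the target day. On ties it says: "In the event that two or more visits are equidistant to the target day, the later visit will be used in the analysis". Table 13 gives Week 24 a target of Day 169 and a window of Days 156 to 183. Table 12.1 fixes the Week 24 pruritus week at Days 163 to 169.

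**What happens at that visit.** Visit 15 is Day 169 ± 3 (SAP Table 7). Responders are re-randomised before dosing, 3:1 to withdrawal or continuation (SAP 3.1). By Table 7 footnote e, the injection follows re-randomisation and is already the new regimen where that differs.

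**The concern.** The boundary between the parts is a dosing day, and the dose given belongs to Part 2. For at least three in four re-randomised patients that dose is placebo. Post-injection safety data are scheduled on the same date: vital signs at 30 minutes and a local skin reaction check (SAP Table 7). Under the period definitions these data fall in Part 1 as well as Part 2.

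The extra day need not be balanced across the Part 1 arms. Only Week 24 responders receive the Day 169 injection in this study. Protocol 3.4 ends follow-up for non-responders outside the LTE at Day 281, 140 days after the last dose, which puts that dose on Day 281 − 140 = Day 141.

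On the efficacy side, EASI, EASI 75, IGA 0/1 and the pruritus response at Week 24 are key secondary endpoints of the placebo-controlled period. Their values should come from before the second randomisation, and the windowing rules do not guarantee that. The SAP protects the corresponding boundary elsewhere: baseline must precede the first dose (4.4.3), and post-dose PK samples, except on four named days, are left out of the summaries (10.2).

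**Working it through.** **1. Reproduce the window.** Table 13 uses midpoints between neighbouring target days. Lower bound: (141 + 169)/2 = 155, so the window opens on Day 156. Upper bound: (169 + 197)/2 = 183. This gives Days 156 to 183, as printed. Nothing in the rule refers to re-randomisation.

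**2. When can a later record replace Visit 15?** Let r be the day of Visit 15 and re-randomisation, from 166 to 172. A record on day d > r replaces it if |d − 169| ≤ |r − 169|, because ties go to the later record. Diary entries after r are the days in 163–169 that exceed r. Post-dose days still mapped to Week 24 number 183 − r.

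| r | distance to 169 | replacing days | number | diary entries after r (of 7) | 183 − r |
|---|---|---|---|---|---|
| 166 | 3 | 167–172 | 6 | 3 | 17 |
| 167 | 2 | 168–171 | 4 | 2 | 16 |
| 168 | 1 | 169–170 | 2 | 1 | 15 |
| 169 | 0 | none | 0 | 0 | 14 |
| 170 | 1 | none | 0 | 0 | 13 |
| 171 | 2 | none | 0 | 0 | 12 |
| 172 | 3 | none | 0 | 0 | 11 |

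The last column matters only if an item was not recorded at Visit 15 and has no nearer record. A post-dose record up to Day 183 could then supply its Week 24 value.

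**3. Where would such a record come from?** No EASI or IGA is scheduled between Visit 15 and Visit 17 (Day 197 ± 3); Visit 16 (Day 176) has neither (SAP Table 8). The record must come from an unscheduled visit or an early termination. IGA is done at every unscheduled clinic visit (SAP 4.4.8), efficacy is assessed before rescue (SAP 7.4), and the early-termination visit includes EASI and IGA (Table 8). The documents give no frequency for these. The diary route needs no extra visit.

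**4. Safety.** Part 1 has 6 dosing days of its own (Days 1, 29, 57, 85, 113, 141). As written, each re-randomised patient adds a seventh, the first Part 2 dosing day, which also opens Part 2.

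**5. Compare with the exposure rule.** With SAP 7.5.1, Part 1 doses on Days 1 to 141 give 141/7 + 4 = 24.1 weeks, and Part 2 doses on Days 169 to 337 give (337 − 169 + 1)/7 + 4 = 28.1 weeks. These fit the listed categories, which reach 28 weeks only for Part 2. Exposure therefore treats the Day 169 injection as a Part 2 dose, while events on that day also count in Part 1.

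**The case against.** The strongest reply is that 4.4.1 already ends Part 1 efficacy at the Week 24 visit, where assessments precede the injection. If the period limits the data first and the windows only label what remains, a record after Visit 15 is a Part 2 record. That is a fair reading. However, 4.4.2 makes Week 24 a windowed analysis visit, and 4.4.1 makes all observed measurements eligible. The text does not say which governs, and a programmer following Table 13 would use the later record.

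The reply is also right on scale. EASI or IGA replacement needs an early Visit 15 and an extra record within days. The diary figure counts entry dates. Entries are ideally made in the morning and look back 24 hours, so the first one after the dose partly describes pre-dose hours.

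Some stronger readings are tempting but unsupported:

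- **A withdrawal flare turns a responder into a Week 24 non-responder.** Days 167 to 172 are 26 to 31 days after a nominal Day 141 dose, about one dosing interval. In the Phase 2a study (protocol 1.4.1.2) the last dose was on Day 85. Among Week 16 IGA 0/1 responders, 12 of 12 on the low dose and 9 of 10 on the high dose had EASI 75 on Day 169, 84 days later. The numbers are small, but they do not suggest loss of response within six days. Continuing patients and placebo responders have no change of regimen.
- **Events are double counted overall.** The Overall summary uses one continuous interval and counts a patient once per preferred term. The duplication is only between the separate Part 1 and Part 2 tables.

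Tables 3 and 4, much of SAP 8.3 and SAP 15.1 are not visible and may contain further handling, notably of rescue.

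**Conclusion.** The point holds, at modest size. The safety overlap follows from the wording: an event starting on the re-randomisation date meets both period definitions, whether it began before or after the injection. If it began after, the Part 1 dose arm is charged with an event that followed a Part 2 injection. One date per re-randomised patient is involved.

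The efficacy part is a conflict between a period that can be read as stopping at Visit 15 and windowing rules that do not stop there. It can matter for EASI and IGA only when Visit 15 is on Days 166 to 168 and an extra record follows, or when an item is missing at Visit 15. EASI and IGA should seldom be missing, because they decide re-randomisation. For pruritus it affects 1 to 3 of 7 entries for those same visit days. Few patients are likely to be affected, and no effect on any treatment comparison is shown. The Week 16 primary endpoint (window Days 100 to 127) is untouched.

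This assumes that Visit 15 stays within its ± 3 days, that the first Part 2 injection is given on the re-randomisation date, and that the unseen SAP text adds no cut-off. The sections relied on (4.4.1, 4.4.2, 9.1 and 15.5) show none.

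**What to change.** For re-randomised patients, state in the SAP:

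- **Visit-based efficacy.** The Week 24 value of EASI, IGA and the other visit-based measures is the last assessment in the window at or before re-randomisation, pre-dose.
- **Pruritus.** The Week 24 mean covers the 7 days up to and including the re-randomisation date. Moving it by up to 3 days makes it share up to 3 diary days with the fixed Week 23 or Week 25 mean, so the SAP should say whether those move too.
- **Week 28.** Keep the window at Days 184 to 211. Label records between re-randomisation and Day 183 as Part 2 unscheduled, still available for the time-to-loss analyses. Opening Week 28 straight after re-randomisation would let a record from, say, Day 170 stand in for a missed Week 28 visit.
- **Safety.** Make the upper bound of Part 1 exclusive of the first Part 2 injection in 4.4.1 and 9.1. Same-day events with onset before the injection go to Part 1; those with onset after it, or at unknown time, go to Part 2 only. Apply the same cut to the Week 24 window in Table 14, so that the 30-minute vital signs count as Part 2.

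The cost is SAP wording and derivation code, with no new data. The downside is that some unknown-time events that began before the injection will be assigned to Part 2. The documents do not say whether event onset time is collected; if it is not, every same-day event goes to Part 2 under this rule.
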